11.3. Appendix 3: Cytochrome P450 3A4 Enzyme Inhibitors and Inducers

Medications that are considered cytochrome P450 3A4 enzyme (CYP3A4) inducers and inhibitors are permitted; however, concomitant administration of strong CYP3A4 inducers or strong inhibitors with the investigational product requires an adjustment to the retosiban dosing regimen (see Protocol Section 5.1 and Section 5.1.1.1).

[figure not shown]
Following is a list of CYP3A4 inhibitors and inducers, each classified as strong, moderate, or weak on the basis of changes in the AUC_i/AUC (area of the curve of substrate in the presence of an inhibitor/area under the curve of substrate in a control condition). This is not an exhaustive list; the summary of product characteristics and/or the package insert for each concomitant medication should be reviewed to determine if the product is a strong CYP3A4 inducer or inhibitor.

Strong ¹ (Requires Adjustment to Dosing Regimen)	Moderate ²	Weak ³
Inhibitors		
Amprenavir	Aprepitant	Amlodipine
Atazanavir	Cimetidine	Atomoxetine
Clarithromycin	Darunavir	Atorvastatin
Conivaptan	Diltiazem	Azithromycin
Fosamprenavir	Erythromycin	Bicalutamide
Grapefruit juice ⁴	Fluconazole	Chlorzoxazone
Indinavir	Imatinib	Cilostazol
Itraconazole	Nifedipine	Cyclosporine
Ketoconazole	Tofisopam	Darifenacin
Nefazodone	Verapamil	Dasatinib
Nelfinavir		Ezetimibe
Ritonavir		Fentanyl
Saquinavir		Fluvoxamine
Telithromycin		Gemfibrozil
Troleandomycin		Isoniazid
Voriconazole		Lacidipine
		Omeprazole
		Posaconazole
		Propiverine

Strong¹ (Requires Adjustment to Dosing Regimen)	Moderate²	Weak³
		Propofol
		Quinidine
		Ranitidine
		Ranolazine
		Roxithromycin
		Tabimorelin
Inducers		
Strong¹ (Requires Adjustment to Dosing Regimen)	Moderate²	Weak³
Carbamazepine	Bosentan	Aprepitant
Efavirenz	Etravirine	Amprenavir
Phenytoin	Nafcillin	Avasimibe
Rifampin	Nevirapine	Dexamethasone
St. Johns Wort	Phenobarbital	Glycyrrhizin
		Modafinil
		Oxcarbazepine
		Pioglitazone
		Prednisone
		Rifabutin
		Rufinamide

1. Strong inhibitor: >5 AUCi/AUC (area of the curve of substrate in the presence of an inhibitor/area under the curve of substrate in a control condition); strong inducer: <0.2 AUCi/AUC. Co-administration of the investigational product with a strong inhibitor or strong inducer requires an adjustment to the retosiban dosing regimen.
2. Moderate inhibitor: 2 to 5 AUCi/AUC; moderate inducer: 0.2 to 0.5 AUCi/AUC.
3. Weak inhibitor: <2 AUCi/AUC; weak inducer: 0.5 to 0.8 AUCi/AUC.
4. The effect of grapefruit juice varies widely among brands and is concentration-, dose-, and preparation-dependent. However, no dose adjustment is needed for retosiban, as grapefruit juice is not expected to cause an interaction given that retosiban is administered intravenously.

11.4. Appendix 4: Safety Reporting Cheat Sheet

AE = adverse event; ARDS = adult respiratory distress syndrome; BDP = bronchopulmonary dysplasia; DIC = Disseminated Intravascular Coagulation; DRE = disease-related event; GERD = gastroesophageal reflux disease; IP = investigational product; IVH = intraventricular hemorrhage; NEC = necrotizing enterocolitis; PDA = patent ductus arteriosus; PPROM = preterm premature rupture of membranes; RDS = respiratory distress syndrome; SAE = serious adverse event.

11.5. Appendix 5: Summary of Human Biological Samples

[Appendix 5](#) categorizes human biological samples as 1) those for which the results are directly related to the conduct and analysis of the study and 2) those collected and stored for future exploratory analyses. Human biological samples directly related to the study conduct and analysis include those for eligibility determination and safety, pharmacokinetics, and placental pathology. Human biological samples collected and stored for biomarker and genetic testing are categorized under future exploratory analyses. [Appendix 5](#) also provides information regarding labeling and subject anonymization. Shipping location information for each sample is provided in the Study Procedures Manual.

The investigator should refer to the laboratory manual for complete information on sample collection and preparation, packaging and labeling, and shipping.

Human Biological Samples Directly Related to the Conduct and Analysis of the Study:

- **Hematology and Chemistry:** Maternal blood samples for hematology and chemistry, including liver function studies, will be collected during Screening, Day 2 of dosing, at the optional retreatment visit (if applicable), and the face-to-face post-infusion assessment visit. Labels will be customized for each test and include the protocol number, subject identification number, visit description, and date and time of collection.
- **Liver Function:** A maternal blood sample for liver function studies will be collected during Screening and sent to the hospital laboratory for analysis. Normal results are required to initiate dosing or continue dosing if dosing has begun before results are available. In the event liver function test results from either the local or central laboratory reveal abnormalities consistent with the liver chemistry stopping criteria defined in Protocol Section [6.3.1](#) and [Appendix 2](#), additional samples will be analyzed for hepatitis A immunoglobulin M (IgM) antibody, hepatitis B surface antigen, hepatitis B core antibody (IgM), cytomegalovirus (CMV) IgM antibody, hepatitis C RNA, hepatitis E IgM antibody, Epstein-Barr viral (EBV) capsid antigen IgM antibody, creatine phosphokinase, lactate dehydrogenase, and complete blood count with differential.

If liver function test results reveal alanine aminotransferase (ALT) $\geq 3 \times$ the upper limit of normal (ULN) AND bilirubin $\geq 2 \times$ ULN ($>35\%$ direct bilirubin; an isolated bilirubin $>1.5 \times$ ULN is acceptable if bilirubin is fractionated and direct bilirubin is $<35\%$) samples will also be analyzed for the following:

- Antinuclear antibody, antismooth muscle antibody, type 1 antiliver kidney microsomal antibodies, and total immunoglobulin G (IgG)
- If chronic hepatitis B is identified at study entry by a positive hepatitis B surface antigen, blood samples will be assayed for hepatitis B DNA and hepatitis delta antibody.
- Serum acetaminophen in subjects with definite or likely acetaminophen use in the preceding week.

Labels will be customized for each test and include the protocol number, subject identification number, descriptor as initial liver event assessment or follow-up, and date and time of collection.

- **Pharmacokinetic Samples:**

1. Maternal blood samples for quantification of retosiban plasma concentrations will be collected 2 to 4 hours, 10 to 14 hours, 22 to 26 hours, and 48 to 54 hours after initiation of the infusion.
2. An umbilical cord blood sample for quantification of retosiban plasma concentrations will be collected in subjects who deliver at the investigational center within 12 hours of investigation product (IP) completion or discontinuation. Additionally, a maternal blood sample should be collected at the same time as the cord blood sample (see Section 6.5.2) if the sample time does not already coincide with one of the PK sampling windows listed above.
3. A breast milk/colostrum sample for a semi-quantitative retosiban assay will be collected in subjects who deliver at the investigational center within 12 hours of IP completion or discontinuation and are expressing breast milk/colostrum.
4. Maternal blood sample for quantification of retosiban plasma concentration within 12 hours of exposure in subjects who meet liver chemistry stopping criteria defined in Protocol Section 6.3.1.

Labels will be customized for each test and include the protocol number, subject identification number, visit description, and date and time of collection.

- **Placental Pathology:** A placental tissue sample will be collected for pathologic examination **when** delivery occurs at an investigational center. Gross examination of the intact placenta, umbilical cord, and membranes will be performed by the hospital pathology department with gross findings reported in a standardized manner. The hospital pathology department will also prepare tissue samples for histologic examination of placenta, membranes, and umbilical cord. Labels will be customized and include the protocol number, subject identification number, visit description, and date and time of collection

Human Biological Samples for Optional Future Biomarker and Genetic Testing:

Biomarker and genetic testing will be performed in relation to the study treatment and preterm labor condition.

- **Biomarker Samples:**

1. Maternal blood samples for biomarker analysis will be collected for all subjects during Screening.
2. An umbilical cord blood sample for biomarker analysis will be collected in subjects who deliver at the investigational center.

Labels will be customized for each test and include the protocol number, subject identification number, visit description, and date and time of collection.

- **Genetic Samples:**

1. Maternal blood samples for genetic analysis will be collected during Screening for subjects who consent to participate. Refer to [Appendix 1](#) for a description of genetic testing objectives, assessments and procedures, subject participation, and confidentiality of data. Labels will be customized for each test and include the protocol number, subject identification number, visit description, and date and time of collection.
2. An umbilical cord blood sample for genetic analysis will be collected in subjects who deliver at the investigational center. Labels will be customized for each test and include the protocol number, subject identification number, visit description, and date and time of collection.

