4.4.1. Withdrawal From Study

4.4.1.1. Withdrawal From Study Participation After Randomization but Prior to Investigational Product Administration

Any subject with a nonreassuring fetal heart rate pattern, a re-assessment that determines tocolytic therapy is no longer indicated (according to investigator's medical discretion), abnormal levels of alanine aminotransferase (ALT) or bilirubin (if results are available), or a clinically significant abnormal finding on an ECG cannot be dosed and should be withdrawn from the study. The reasons for not dosing a subject will be recorded in the eCRF and source documents. Subjects who are withdrawn prior to receiving randomized IP will not be followed.

A nonreassuring fetal heart rate is defined as either unresolved Category 3 tracings (including either [1] the absence of baseline fetal heart rate variability and any of the following: recurrent late decelerations, recurrent variable decelerations, or bradycardia; or [2] sinusoidal pattern) or at the investigator's discretion.

Dosing may be started before local liver function test results are available; however, if local laboratory results are available before the start of dosing and ALT is $>2 \times$ the upper limit of normal (ULN) or bilirubin is $>1.5 \times$ ULN ($>35\%$ direct bilirubin), the subject should not be dosed and should be withdrawn from the study. An isolated bilirubin $>1.5 \times$ ULN is acceptable if bilirubin is fractionated and direct bilirubin is $<35\%$. See Section 6.3.1 for liver stopping criteria for management of abnormal test results that become available after the start of dosing.

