6.3.1. Liver Chemistry Stopping and Follow-Up Criteria

Blood samples will be collected for central laboratory evaluation at Screening (prior to treatment), during Day 2 of the randomized treatment phase, and at the face-to-face post-infusion assessment visit for additional liver function testing in order to ensure subject safety and to evaluate liver event etiology (in alignment with the US Food and Drug Administration premarketing clinical liver safety guidance); <http://www.fda.gov/downloads/Drugs/GuidanceComplianceRegulatoryInformation/Guidances/UCM174090.pdf>.

At Screening, before IP administration, ALT and bilirubin test results from a local laboratory should be obtained, although dosing may be started prior to the availability of these results. However, if the local laboratory results are available before the start of dosing and meet the following criteria, the subject should not be dosed and should be withdrawn from the study:

[figure not shown]
- ALT $\geq 2 \times$ ULN OR bilirubin $> 1.5 \times$ ULN ($> 35\%$ direct bilirubin). An isolated bilirubin $> 1.5 \times$ ULN is acceptable if bilirubin is fractionated and direct bilirubin is $< 35\%$.

Phase III-IV liver chemistry stopping criteria are presented in [Figure 3](#) and [Appendix 2](#).

The local and central laboratory liver function test results should be reviewed for the abnormalities shown in [Figure 3](#). If the laboratory results are not available at the start of dosing and subsequent local OR central laboratory results are abnormal, dosing may be continued at the discretion of the investigator, as long as they do not exceed the liver chemistry stopping criteria shown in [Figure 3](#) and detailed in [Appendix 2](#).

NOTE: The central laboratory report will include results for ALT, aspartate aminotransferase (AST), alkaline phosphatase (ALP), total bilirubin, and direct bilirubin.

Figure 3 Phase III-IV Liver Chemistry Stopping and Increased Monitoring Algorithm

ALT = alanine aminotransferase; INR = international normalized ratio; SAE = serious adverse event; ULN = upper limit of normal.

The complete Liver Safety Required Actions and Follow-up Assessments section can be found in [Appendix 2](#).

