6.3.11. Prompt Reporting of SAEs and Other Events to GSK/PPD

Serious AEs, nonserious AEs related to study treatment, and liver function abnormalities meeting predefined criteria will be reported promptly by the investigator to GSK/PPD as described in Table 6 once the investigator determines that the event meets the protocol definition for that event. Additional details describing DREs not qualifying as SAEs are described in Section 6.3.7.

Table 6 Reporting of Serious Adverse Events and Other Events to GSK/PPD

Type of Event	Initial Reports		Follow-up Information on a Previous Report	
	Time Frame	Documents	Time Frame	Documents
All SAEs	24 hours	“SAE” data collection tool	24 hours	Updated “SAE” data collection tool
Cardiovascular or death event	Initial and follow-up reports to be completed within 1 week of when the cardiovascular event or death is reported	“CV events” and/or “death” data collection tool(s) if applicable	Initial and follow-up reports to be completed within 1 week of when the cardiovascular event or death is reported	Updated “CV events” and/or “death” data collection tool(s) if applicable
Nonserious adverse events related to study treatment	5 calendar days	“Adverse Reaction” data collection tool	2 weeks	Updated “Adverse Reaction” data collection tool
DRE	2 weeks ¹	DRE eCRF	2 weeks ¹	Updated DRE eCRF
Liver chemistry abnormalities				
ALT \geq 3 x ULN and bilirubin \geq 2 x ULN (>35% direct) (or ALT \geq 3 x ULN and INR>1.5, if INR measured) ²	24 hours ³	“SAE” data collection tool, “Liver Event eCRF” and “Liver Imaging” and/or “Liver Biopsy” eCRFs, if applicable ⁴	24 hours	Updated “SAE” data collection tool/“Liver Event” Documents ⁴
ALT \geq 8 x ULN; ALT \geq 3 x ULN with hepatitis or rash or \geq 3 x ULN and <5 x ULN that persists \geq 4 weeks	24 hours ³	“Liver Event” Documents (defined above) ⁴	24 hours	Updated “Liver Event” Documents ⁴

ALT = alanine aminotransferase, CV = cardiovascular; DRE = disease-related event, eCRF = electronic case report form; GSK = GlaxoSmithKline; INR = International normalized ratio, SAE = serious adverse event, ULN = upper limit of normal.

1. The study review team should determine the appropriate time frame, if one is needed, for completion of DRE eCRF pages
2. The INR measurement is not required; if measured, the threshold value stated will not apply to subjects receiving anticoagulants.
3. GSK/PPD must be contacted at onset of liver chemistry elevations to discuss subject safety.

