11.2. Appendix 2: Liver Chemistry Stopping and Follow-up Criteria

Liver Chemistry Stopping Criteria - Liver Stopping Event	
ALT-Absolute	ALT $\geq 8 \times$ ULN
ALT-Increase	ALT $\geq 5 \times$ ULN but $< 8 \times$ ULN persists for ≥ 2 weeks ALT $\geq 3 \times$ ULN but $< 5 \times$ ULN persists for ≥ 4 weeks
Bilirubin^{1,2}	ALT $\geq 3 \times$ ULN and bilirubin $\geq 2 \times$ ULN ($> 35\%$ direct bilirubin)
INR²	ALT $\geq 3 \times$ ULN and INR > 1.5 , if INR measured
Cannot Monitor	ALT $\geq 5 \times$ ULN but $< 8 \times$ ULN and cannot be monitored weekly for ≥ 2 weeks ALT $\geq 3 \times$ ULN but $< 5 \times$ ULN and cannot be monitored weekly for ≥ 4 weeks
Symptomatic³	ALT $\geq 3 \times$ ULN associated with symptoms (new or worsening) believed to be related to liver injury or hypersensitivity
Required Actions and Follow-up Assessments Following ANY Liver Stopping Event	
Actions	

 Immediately discontinue study treatment Report the event to GSK/PPD within 24 hours Complete the liver event eCRF and complete an SAE data collection tool if the event also meets the criteria for an SAE² Perform liver event follow-up assessments Monitor the subject until liver chemistries resolve, stabilize, or return to within baseline (see MONITORING below) Do not restart/rechallenge subject with study treatment but continue subject in the study for any protocol-specified follow-up assessments 	
Follow-up Assessments	

 Viral hepatitis serology⁴ Only in those with underlying chronic hepatitis B at study entry (identified by positive hepatitis B surface antigen) quantitative hepatitis B DNA and hepatitis delta antibody⁵ A blood sample for pharmacokinetic analysis will be obtained within 12 hours of last dose (completion or discontinuation)⁶ Serum creatine phosphokinase and lactate dehydrogenase Fractionated bilirubin, if total bilirubin $\geq 2 \times$ ULN Obtain complete blood count with differential to assess eosinophilia Record the appearance or worsening of clinical symptoms of liver injury, or hypersensitivity, on the AE report form Record use of concomitant medications on the concomitant medications report form 	

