
ALT $\geq 5 \times$ ULN and $< 8 \times$ ULN and bilirubin $< 2 \times$ ULN without symptoms believed to be related to liver injury or hypersensitivity, and who can be monitored weekly for 2 weeks.
 
OR
 
ALT $\geq 3 \times$ ULN and $< 5 \times$ ULN and bilirubin $< 2 \times$ ULN without symptoms believed to be related to liver injury or hypersensitivity, and who can be monitored weekly for 4 weeks.
	
 Notify the PPD medical monitor within 24 hours of learning of the abnormality to discuss subject safety. Subject can continue study treatment Subject must return weekly for repeat liver chemistries (ALT, AST, alkaline phosphatase, bilirubin) until they resolve, stabilize, or return to within Baseline If at any time subject meets the liver chemistry stopping criteria, proceed as described above If ALT decreases from ALT $\geq 5 \times$ ULN and $< 8 \times$ ULN to $\geq 3 \times$ ULN but $< 5 \times$ ULN, continue to monitor liver chemistries weekly. If, after 4 weeks of monitoring, ALT $< 3 \times$ ULN and bilirubin $< 2 \times$ ULN, monitor subjects twice monthly until liver chemistries normalize or return to within baseline.

ALT = alanine aminotransferase; AST = aspartate aminotransferase; GSK = GlaxoSmithKline; ULN = upper limit of normal.

References

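### Appendix 5 and Section 6.3.1 give opposite rules on continuing the infusion when a late Screening liver result is abnormal but below the stopping criteria

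*Protocol*

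**What the plan says.** **Continuing after dosing has begun.** The liver function item of Protocol Appendix 5 describes the maternal sample taken at Screening and sent to the hospital laboratory, and states: "Normal results are required to initiate dosing or continue dosing if dosing has begun before results are available". Section 6.3.1 deals with results that were not available at the start and later prove abnormal, whether local or central: "dosing may be continued at the discretion of the investigator, as long as they do not exceed the liver chemistry stopping criteria". Appendix 2 has an increased-monitoring band: ALT from 3 to below 8 x ULN, bilirubin below 2 x ULN, no relevant symptoms, and weekly monitoring possible. Its instruction for that band is "Subject can continue study treatment". Section 4.4.2 (item 6) refers discontinuation for abnormal liver tests back to the Section 6.3.1 criteria.

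**Starting.** Section 4.4.1.1 withholds dosing when "ALT is $>2 \times$ the upper limit of normal (ULN". Section 6.3.1 gives the limit as "ALT $\geq 2 \times$ ULN OR bilirubin $> 1.5 \times$ ULN" (with more than 35% direct bilirubin). Section 6.1 and Table 5 footnote 16 use the same inclusive ALT limit as Section 6.3.1.

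**Reporting.** Appendix 2 says of any liver stopping event: "Report the event to GSK/PPD within 24 hours". Table 6 in Section 6.3.11 lists particular liver abnormalities for 24-hour reporting. Besides the row combining ALT with bilirubin or INR, it covers ALT ≥8 x ULN, ALT ≥3 x ULN "with hepatitis or rash or" ALT 3 to below 5 x ULN lasting at least 4 weeks.

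**The concern.** Sections 4.4.1.1, 6.1 and 6.3.1 all let the infusion start before the local result is known, so an abnormal result arriving mid-infusion is foreseeable. On that result, a site reading Appendix 5 would stop the infusion, while a site reading Section 6.3.1 may continue it. Section 3.1 allows no protocol waivers except for immediate safety concerns, so whichever course a site takes can be called a deviation under the other passage.

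The first matter at stake is the safety of an individual woman, since this rule decides whether an experimental infusion runs on. The second is the consistency of the data. SAP Section 6.2 reports discontinuation of investigational product with reasons by arm, and SAP Section 4.1 lists significant protocol deviations. Both would depend partly on which passage a site had followed.

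**Working it through.** There is no figure to recompute. The check is whether the current passages can be read together.

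**1. Is the Appendix 5 sentence current?** Yes. It stands in Section 11.5. The Amendment 04 entry in Appendix 6 only repeats it.

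**2. Which results does it cover?** It sits in the liver function item and follows the description of the local Screening sample. The central samples (Screening, Day 2, retreatment, post-infusion visit) are under a separate haematology and chemistry item, which has no requirement for normal results.

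**3. The rules compared by ALT level:**

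| Situation | Appendix 5 | Other sections |
|---|---|---|
| Result known before dosing, ALT above ULN but below 2 x ULN | Not normal, so no dosing on a literal reading | Below the limit in 4.4.1.1, 6.1, 6.3.1 and Table 5 |
| Result known before dosing, ALT exactly 2 x ULN | Not normal | 4.4.1.1 does not bar dosing; 6.1, 6.3.1 and Table 5 do |
| Result arrives during infusion, ALT above ULN but below 3 x ULN | May not continue | 6.3.1: may continue at discretion (every Appendix 2 stopping criterion needs ALT of at least 3 x ULN) |
| Result arrives during infusion, ALT 3 to below 8 x ULN, bilirubin below 2 x ULN, no symptoms, can be monitored, no INR criterion met | May not continue | 6.3.1 and Appendix 2: may continue |
| Any stopping criterion met | May not continue | Stop |

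Only the third and fourth rows are direct contradictions about a running infusion.

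**4. Can a loose reading of normal remove the conflict?** Appendix 5 does not define the word.
- If it means within the laboratory range, the conflict runs from just above ULN up to the stopping criteria.
- If it is shorthand for the pre-dose limits, the starting conflict disappears. The continuing conflict remains from about 2 x ULN up to the stopping criteria.
- It vanishes only if normal means anything short of a stopping criterion. Section 6.3.1 rules that out, because it calls such results abnormal when it permits continuation.

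**5. Upper edge of the band.** It is not a single ALT value. ALT ≥8 x ULN always stops treatment. From 3 x ULN, treatment also stops with bilirubin ≥2 x ULN (more than 35% direct), INR above 1.5 if measured, relevant symptoms, or inability to monitor weekly. Persistence is a further criterion: at least 4 weeks for 3 to below 5 x ULN, and at least 2 weeks for 5 to below 8 x ULN.

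**6. Table 6 against Appendix 2.** Table 6 has no row for ALT 5 to below 8 x ULN lasting at least 2 weeks, nor for the two criteria on inability to monitor, although it lists the milder 3 to below 5 x ULN lasting at least 4 weeks. Its symptom wording also differs from that of Appendix 2, which refers to symptoms thought related to liver injury or hypersensitivity.

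**The case against.** The best defence is that Appendix 5 is an inventory of samples and their labelling, not a dosing section. The sections that do govern dosing agree with one another: 4.4.1.1, 4.4.2 and Table 5 footnote 16 all lead to 6.3.1, and Appendix 2 is consistent with it. Appendix 5 itself cites 6.3.1 and Appendix 2 in its next sentence. On this view there is one stray sentence rather than two competing rule sets. That is a fair account of how the conflict probably arose, and many sites would follow 6.3.1. But the sentence is an unqualified requirement in current protocol text, and nothing says that 6.3.1 overrides it.

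The objection succeeds on three further points.

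- **Scope.** A reader might infer that every abnormal result returned during infusion is caught, up to 8 x ULN. The documents do not support this. The Appendix 5 rule attaches to the local Screening sample only, and several stopping criteria apply from 3 x ULN.
- **Under-reporting.** A reader might infer that Table 6 would leave a more severe liver event unreported. Table 6 footnote 3, attached to both liver rows, requires contact with the sponsor or its contract organisation at the onset of liver chemistry elevations. Appendix 2 requires the medical monitor to be told within 24 hours once ALT is in the increased-monitoring band, before any persistence criterion can be met, and separately requires 24-hour reporting of any stopping event. The omission is a drafting gap with limited consequence. Persistence over 2 to 4 weeks has little bearing on a 48-hour infusion. It could bear on a second course, since retreatment is allowed (Section 3.1.3.1) and restart after a stopping event is not (Section 6.3.1.1).
- **The inequality sign.** Three of the four places agree, and the difference matters only at exactly 2 x ULN.

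Finally, the SAP synopsis says that the study was terminated for feasibility with 97 patients enrolled, so rewording would change no future dosing in this trial if recruitment is closed.

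**Conclusion.** The contradiction on continuing the infusion is real and cannot be read away. It affects women whose local Screening liver result arrives after the infusion starts and is abnormal but below the stopping criteria, which depend on ALT, bilirubin, INR, symptoms and ability to monitor. The documents give neither the frequency of abnormal Screening results nor the share that arrive late, so no count can be offered. The rule on starting is a weaker part of the point, because normal may there be shorthand for the pre-dose limits.

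The pre-dose inequality and the Table 6 rows are secondary inconsistencies. They do not show that sites would under-report liver events.

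Nothing here touches sample size, power or type I error. Under Section 4.4.2, women who discontinue investigational product stay in follow-up and in the ITT population. The analytic consequence is limited to discontinuation reasons and the classification of deviations.

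The conclusion rests on the text of Appendix 5, Section 6.3.1 and Appendix 2. Figure 3, the stopping algorithm to which Section 6.3.1 refers, was not available to check.

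**What to change.** - Reconcile Appendix 5 with Section 6.3.1 and Appendix 2 so that one rule governs continuation after a late abnormal result. State it in one place and cross-refer from the others. If the word normal is kept, define it.
- Use a single pre-dose ALT limit in Sections 4.4.1.1, 6.1, 6.3.1 and Table 5 footnote 16.
- Make the liver rows of Table 6 match the Appendix 2 stopping events, including their symptom wording, or replace the rows with a reference to Appendix 2.

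Which rule and which limit should stand is a clinical decision for the sponsor, and none is proposed here. The cost is protocol wording only: no new assessments, data or analyses. If the protocol will not be amended because the study has ended, record before unblinding which passage was applied when deviations and treatment discontinuations were classified, and correct the text before it is reused in another protocol.
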